9.4 Safety Assessments

Safety measures include:

- Subject responses on the validated FACE-Q Recovery Early Life Impact questionnaire ([Klassen 2015](#); 12 items scored in the same manner as the first secondary effectiveness measure)
- Subject assessment of procedural pain at initial treatment on an 11-point scale ranging from 0 (no pain) to 10 (worst pain imaginable)
- Subject assessment of the presence and severity of ISRs, recorded in the subject's daily e-diary for each cheek for up to 30 days after treatment (initial, touch-up, and repeat) starting on the day of treatment
- AEs from TI observation and inquiry at scheduled follow-up visits
- Monitoring of concomitant medications and concurrent procedures
- Snellen visual acuity assessed by the TI (or designee)
- Confrontational visual fields assessed by the TI (or designee)
- Ocular motility assessments assessed by the TI (or designee)

The subject's daily safety e-diary will list the following ISRs that have been reported previously with HA dermal filler injections and will include space to include other symptoms:

- Redness
- Pain after injection
- Sensitivity to touch
- Firmness
- Swelling
- Lumps/bumps
- Bruising
- Itching
- Discoloration (not redness or bruising)

The subject's daily safety e-diary will list the following severities for ISRs to be recorded:

None	None or not applicable.
Mild	Symptoms causing little, if any, discomfort leading to little, if any, effect on daily activities.
Moderate	Symptoms causing some discomfort leading to some effect on daily activities.
Severe	Symptoms causing great discomfort leading to compromised performance of daily activities.

Subjects are to bring the e-diaries to their Day 3 and Day 30/Month 1 visits for review by the TI, and the TI will determine if the ISR qualifies as an AE. ISRs that are ongoing at the end of the diary will be reported on the ongoing ISR eCRF and tracked to resolution or until follow-up is no longer possible. Subjects who did not record the e-diaries for the entire diary period are to enter the responses on the Day 30/Month 1 visits to ensure a consistent recording between eCRF and e-diaries.

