10.3.2 Safety Analyses

The following safety categories will be summarized as appropriate for the safety population and will be fully defined in the SAP.

- FACE-Q Recovery Early Life Impact questionnaire
- Subject assessment of procedural pain
- ISRs
- AEs

- Snellen visual acuity, confrontational visual fields, and ocular motility assessments

FACE-Q Recovery Early Life Impact questionnaire and procedural pain will be summarized by frequency distributions or descriptive statistics.

ISRs reported by subjects will be summarized using descriptive statistics, by symptom, maximum reported severity, and duration for initial, touch-up, and repeat treatments, separately.

Incidence of AEs will be summarized by primary system organ class, preferred term, and severity. Additionally, a summary will be tabulated by onset, duration, severity, action taken, relationship to treatment, and outcome. The summary will include incidence rate as well as total number of events.

Treatment-related AEs, SAEs, AEs leading to study discontinuations, and deaths will be listed or tabulated. All pre-treatment AEs will be listed but not summarized.

Snellen visual acuity, confrontational visual fields, and ocular motility assessments will be summarized descriptively.

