5.6.4. Injection Site Response

ISRs recorded in participant diaries after each treatment (initial, touch-up or repeat) and the ongoing ISR e-CRF will be summarized. The diary date and time will be compared with the treatment injection date and time recorded in the database to determine the corresponding treatment (ie, initial, touch-up, or repeat) for the purpose of analysis. If there are multiple diary entries of the same treatment period for any day, then the worse severity and maximum duration

JUVÉDERM VOLITE™ XC

will be included in the summary for the corresponding symptom(s) analyzed. The descriptive statistics will be tabulated for the endpoints listed in Table 5-9 for the initial treatment, touch-up treatment, and repeat treatment periods by pre-defined symptoms.

Table 5-9 **Injection Site Response Analyses**

Endpoint	Description	Timing	Methodology
ISR severity	
Maximum reported severity for 2 summaries listed below:
 
 Up to 30 days after the treatment (initial, touch-up or repeat) based on diary data only Beyond 30 days after the (initial, touch-up or repeat) treatment across the diary and ongoing ISR eCRF 	Initial, Touch-up, Repeat	Frequency counts and percentages
ISR duration	
Duration from first instance of the symptom to the last instance of the symptom within the treatment period for 2 summaries listed below:
 
 Up to 30 days after the treatment (initial, touch-up or repeat): duration is derived as date of last ISR minus date of first ISR plus one based on the diary data between the date of corresponding treatment and 30 days after it on the participant level, regardless of the side of cheek. Beyond 30 days after the (initial, touch-up or repeat) treatment: duration is calculated as the last minus the first ISR occurrence date plus one based on all data collected from diary and ongoing ISR eCRF. 	Initial, Touch-up, Repeat	Frequency counts and percentages

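### ISR duration up to 30 days is a first-to-last span over both cheeks, so symptom-free days between reports are tabulated as duration

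*SAP*

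**What the plan says.** Protocol Section 9.4 has participants assess the presence and severity of each ISR, "recorded in the subject's daily e-diary for each cheek for up to 30 days after treatment", and the severity list includes an explicit None. Protocol Section 10.3.2 asks for ISRs to be summarized "by symptom, maximum reported severity, and duration for initial, touch-up, and repeat treatments, separately", without defining duration. The SAP therefore holds the only definition.

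SAP Table 5-9 describes the measure as "Duration from first instance of the symptom to the last instance of the symptom within the treatment period". The row up to 30 days adds the formula, "duration is derived as date of last ISR minus date of first ISR plus one based on the diary data", takes the data "between the date of corresponding treatment and 30 days after it", and works "on the participant level, regardless of the side of cheek". The row beyond 30 days adds the ongoing-ISR eCRF and keeps the span rule, "duration is calculated as the last minus the first ISR occurrence date plus one", but does not say whether cheeks are combined. Results are tabulated "for the initial treatment, touch-up treatment, and repeat treatment periods by pre-defined symptoms", as frequency counts and percentages.

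Section 5.6.4 has no rule for symptom-free days between reports, for separate episodes, for missed diary days or for duration on each cheek.

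**The concern.** The diary yields a daily record for each cheek, and the derivation keeps two dates from it. A response present throughout and a brief response with one late or recurrent report get the same figure when their first and last dates agree. Combining the cheeks adds a second way to lengthen the span, because a report on one side can extend a response that ended on the other.

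ISRs are a listed safety endpoint, and duration is one of the two ISR results in Table 5-9. A reader of a row headed duration will take it as how long the response lasted. The long-duration categories, which matter most to a safety reader, are the ones most sensitive to a single late entry.

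**Working it through.** The documents give no ISR duration figure to reproduce, so the check applies the rule to example diaries and then shows how the result depends on late reports.

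**Rule.** For one symptom after one treatment, pool the report dates of both cheeks. Duration = last day − first day + 1. SAP 5.6.4 numbers the treatment date as Day 1, so 30 days after treatment is Day 31.

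**Example diaries, all days completed.**

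| Reports of one symptom | SAP span | Days reported, either cheek | Days reported, longer cheek |
|---|---|---|---|
| Both cheeks, Days 1-5 | 5 − 1 + 1 = 5 | 5 | 5 |
| One cheek, Days 1-3 and Day 20 | 20 − 1 + 1 = 20 | 4 | 4 |
| Left Days 1-3, right Days 25-26 | 26 − 1 + 1 = 26 | 5 | 3 |
| Left Days 1-3, right Day 28 | 28 − 1 + 1 = 28 | 4 | 3 |

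With no gap, the measures agree. The second row shows the effect of a gap alone. The last two show the added effect of joining the cheeks.

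**Sensitivity to late reports.** Assumptions, none of them from the documents: a true response on Days 1-5; then an isolated report of the same symptom with probability q per cheek-day on Days 6-31, constant and independent; a complete diary. Table 5-9 gives frequencies but does not list its categories, so 14 days is used as an illustrative cut.

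- Days 15-31 are 17 days, or 34 cheek-days. Share with a span over 14 days, cheeks combined: 1 − (1 − q)^34.
- The same for a single cheek: 1 − (1 − q)^17.
- Expected days with the symptom on either cheek: 5 + 26 × [1 − (1 − q)^2].

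| q per cheek-day | Span > 14 days, cheeks combined | Span > 14 days, one cheek | Expected days with symptom |
|---|---|---|---|
| 0 | 0% | 0% | 5 |
| 0.2% | 6.6% | 3.3% | 5.10 |
| 0.5% | 15.7% | 8.2% | 5.26 |
| 1% | 28.9% | 15.7% | 5.52 |

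Combining the cheeks roughly doubles the share over 14 days. By a count of days, exceeding 14 would need at least 10 late days out of 26, against an expected 0.52 at q = 1%, so that share is effectively zero.

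**Cross-check.** A simulation of 100,000 diaries per setting, with a 3-day response and follow-up to Day 30, gave 14.9% and 27.6% over 14 days by the span rule at q = 0.5% and 1%, and 0.0% by days reported. The formula for those settings, 1 − (1 − q)^32, gives 14.8% and 27.5%.

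**Missed entries.** Protocol Section 9 says the e-diary locks past days, so a gap may be a missed entry. Take a true response on Days 1-5 with Days 3-4 not entered. The span gives 5. A bare count of diary days gives 3, and the longest run allowing a 1-day gap gives 2. A count that treats the two missed days as symptomatic, because they lie between symptomatic entries on the same cheek, gives 5.

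**The case against.** The strongest reply is that this is a disclosed and defensible measure. The SAP says openly that it runs from first to last instance, never calls it continuous, and contradicts nothing in the protocol. Time until a symptom is last seen matters to patients. Late reports need not be noise: Protocol Section 9.5 lists delayed effects, including intermittent swelling. The span cannot hide a long response, and it bridges missed entries that a simple count would lose. All of this stands, and it is why the span should stay in the table.

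A reader might go further and infer that unrelated reactions are being joined. The documents do not support that in general. Summaries are by symptom and by treatment, so only reports of the same symptom after the same treatment are linked. The possible exception is the Other symptoms row, where a participant with several different terms is counted once.

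A reader might also carry the cheek criticism over to the row beyond 30 days. That row shares the span rule but does not state pooling.

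The percentages above are also open to challenge. The late-report rate is assumed, and holding it constant to Day 31 makes a new report as likely late as early. They show sensitivity and do not predict this trial's results.

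The reply leaves one matter unanswered: a cautious figure still cannot tell a persistent response from a brief one with a late report, although the data to do so are collected.

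**Conclusion.** The point holds as a limitation of a descriptive safety summary. Up to 30 days, Table 5-9 counts symptom-free days and reports of the same symptom on opposite cheeks as duration. Relative to days recorded with the symptom, the figure can only be equal or higher. The row beyond 30 days has the gap problem; cheek pooling there is unspecified.

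The size is unknown. It is zero if there are no late reports. Under the stated assumptions, 6.6% to 28.9% of participants with a 5-day response would be shown with more than 14 days for q between 0.2% and 1%.

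It would be wrong to conclude that the plan flatters the product or that a trial conclusion is at risk. The rule lengthens duration, no hypothesis test uses it, and effectiveness is untouched. Nor do the documents support dropping the span: a plain count of diary days could understate duration where entries were missed.

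**What to change.** In SAP Table 5-9:

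- Keep the prespecified span and label it *days from first to last report*.
- Add, in the same frequency-category format, the number of days with the symptom, derived for each cheek with the longer cheek taken at participant level.
- Count missed diary days lying between two symptomatic entries on the same cheek as symptomatic, and treat only days recorded as None as symptom-free. Missed entries inside a response then do not shorten it. Missed days after the last report are counted by neither measure.
- State whether the row beyond 30 days combines cheeks.

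The added row reports the longer cheek, so a response that moves from one side to the other appears shorter there than in the span. Showing both rows together covers this. The cost is one extra row per symptom and a little more programming on data already collected.

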Other symptoms of ISR entered in the e-diary by participants will be coded into medical terminologies by the medical safety physician. Other ISRs with “No”, “None”, or texts with a similar meaning will be coded as “n/a”. If other ISRs are coded as one of the prespecified symptoms (ie., redness, pain after injection, tenderness to touch, firmness, lumps/bumps, bruising, itching, and discoloration), then the participant will be counted only once based on the maximum severity and duration across the pre-specified symptom entries and the coded terms. Other symptoms of ISR that were coded into the terms beyond the list of pre-specified symptoms will be summarized under “Other symptoms” in the summary tables for ISR. If a participant reported more than one non-prespecified terms of “other ISR”, the participant will be counted once in the summary of “Other symptoms” for that treatment. The free texts entered by the participant, and the coded terms for “other symptoms” will be included in the data listing.

ISR day will be derived as ISR date – most recent treatment date + 1.

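### SAP 5.6.4 omits swelling from the symptom list used to merge recoded free-text injection site responses, so free text coded as swelling is routed to the Other symptoms category

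*SAP*

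**What the plan says.** Protocol 9.4 (Safety Assessments) fixes the content of the ISR diary: "The subject's daily safety e-diary will list the following ISRs that have been reported previously with HA dermal filler injections". Nine named symptoms follow, with swelling between firmness and lumps/bumps, and there is space for other symptoms. The touch item is labelled "Sensitivity to touch". Protocol 10.3.2 commits to summarizing ISRs by symptom, maximum severity and duration, separately for each treatment.

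SAP 5.6.4 (Injection Site Response) carries this out in two steps.

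- **Tables.** Descriptive statistics are produced "for the initial treatment, touch-up treatment, and repeat treatment periods by pre-defined symptoms". The sentence does not say which symptoms those are.
- **Free text.** Symptoms typed in by participants are coded by the medical safety physician. If the code is one of the prespecified symptoms, given as "redness, pain after injection, tenderness to touch, firmness, lumps/bumps, bruising, itching, and discoloration", the participant is counted once, at the maximum severity and duration over the ticked entries and the coded terms. For anything else, the rule is: "Other symptoms of ISR that were coded into the terms beyond the list of pre-specified symptoms will be summarized under" the Other symptoms heading, with one count per participant per treatment however many such terms were reported.

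The free text and its codes are also kept in a data listing.

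**The concern.** The list in the free-text rule decides where each coded entry goes, so an omission from it changes counts. Swelling is an expected response to this procedure: protocol 3.4 names it among the risks common to filler injection, and protocol 9.5 lists it among the known potential adverse events. If a participant describes swelling in words and the entry is coded as swelling, the rule as written does not treat it as a prespecified symptom.

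At stake is the accuracy of the swelling summary (incidence, maximum severity and duration), and the meaning of the Other symptoms row, which would then contain a response that the diary already names.

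**Working it through.** The plan states no figure for this point, so the check is a comparison of the two lists followed by a literal application of the rule.

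**Step 1: the lists side by side**

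| Protocol 9.4 e-diary | SAP 5.6.4 prespecified list | Match |
|---|---|---|
| Redness | redness | yes |
| Pain after injection | pain after injection | yes |
| Sensitivity to touch | tenderness to touch | different label |
| Firmness | firmness | yes |
| Swelling | (absent) | **no** |
| Lumps/bumps | lumps/bumps | yes |
| Bruising | bruising | yes |
| Itching | itching | yes |
| Discoloration, with a qualifier excluding redness and bruising | discoloration | yes, label shortened |

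The count is 9 diary items against 8 SAP items: 7 match (one with a shortened label), 1 is renamed and 1 is missing (7 + 1 + 1 = 9). The SAP sentence runs unbroken from firmness to lumps/bumps, so nothing suggests a redaction or a gap in the text.

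**Step 2: apply the rule to free text coded as swelling**

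Swelling is not on the list, so the entry is beyond it and goes to Other symptoms. The merge at maximum severity and duration is not triggered. Assume the tables do have a swelling row, fed by the ticked diary item.

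- *Swelling not ticked, free text coded as swelling.* The participant is missing from the swelling row and appears under Other symptoms. Swelling incidence is understated by that participant.
- *Swelling ticked, free text coded as swelling.* The participant is in the swelling row through the tick and in Other symptoms through the text, so one symptom is counted in two rows.
 - Severity: merging would give max(s_tick, s_text), while the rule as written gives s_tick. They differ only if s_text > s_tick.
 - Duration: Table 5-9 defines it as last date minus first date plus one. With ticked entries from day a to day b and free text from day c to day d, the span over both sources is max(b, d) − min(a, c) + 1, against b − a + 1 as written. They differ only if c < a or d > b.
- *Participant already has another nonlisted term.* Other symptoms is counted once per participant per treatment, so the misrouted entry does not raise that row further.

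**Step 3: the table rows**

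The instruction to tabulate "repeat treatment periods by pre-defined symptoms" does not refer to the list in the free-text rule, and the SAP names the ISR symptoms nowhere else. Two readings are open: the nine diary items, which keep the swelling row, or the eight listed items, which do not. SAP Section 1 places the table specifications in a separate document, so the text cannot settle which applies.

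**The case against.** The strongest defence is that the eight-item parenthesis belongs to a rule about free text and was never presented as the list of table rows. A ticked swelling item is not an other symptom, so nothing in the rule moves it. The SAP describes itself as elaborating the protocol, and the protocol's diary has swelling as a structured item. Read together, the natural meaning of predefined symptoms is the diary's nine. The list also looks like a loose paraphrase: it renames one item and shortens another. Most swelling data should come from ticked entries, free text and codes are listed, and the treating investigator reviews the diaries and decides whether an ISR is an adverse event.

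Most of this stands, and it limits the point. A reader might infer that swelling disappears from the by-symptom ISR tables altogether. The documents do not support that, for the reasons just given and because the table specifications are not available. Nor is it right to say flatly that swelling severity and duration will be understated: Step 2 shows that this happens only under stated conditions.

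What does not stand is the idea that the omission has no effect. The list is the operative test for merging or not merging, and it is introduced as a complete list. A programmer who follows it will misroute free text coded as swelling. The data listing preserves the entries but does not correct the summary tables. SAP Appendix 2 records that the coded-term analysis was added in the current version and gives no reason for leaving swelling out, so an oversight is the likely explanation.

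**Conclusion.** The point holds as a minor inconsistency between protocol and SAP: the merge rule in SAP 5.6.4 is wrong as written for one of the nine diary symptoms, and a second carries a different name. The consequence that follows from the text is that free text coded as swelling is summarized under Other symptoms. Swelling incidence, severity or duration can then be understated, and a participant can be counted twice.

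The size is probably small. It depends on how often participants describe swelling in words although the diary offers a swelling item, and the documents give no basis for a number. Only descriptive safety tables are affected. No hypothesis test, sample size or effectiveness result changes.

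The conclusion assumes that the SAP list is applied literally and that the separate specifications do not already correct it. If those specifications take their rows from this list, the swelling row would be lost as well. That is a possibility to check, not a finding.

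**What to change.** In SAP 5.6.4:

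1. Add swelling to the prespecified symptoms in the free-text rule.
2. Use the diary's labels throughout, in particular for the touch item and the full discoloration label.
3. State that the predefined symptoms used for the ISR tables are the nine e-diary items in protocol 9.4, with Other symptoms as a separate row.

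Check the table specifications against the same nine items. The cost is one corrected line and one added sentence in the SAP. No new data collection, protocol change or change to any tested analysis is needed.

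### The ISR summary tables give no per-term rate for unlisted reactions, and the rule for merging free text into a listed symptom does not agree with the Table 5-9 definition of duration

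*SAP*

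**What the plan says.** Protocol 9.4 lists nine symptoms in the daily e-diary and adds that the diary "will include space to include other symptoms". Protocol 10.3.2 plans to summarize ISRs by symptom, with maximum severity and duration, separately for initial, touch-up and repeat treatment.

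SAP 5.6.4 has the medical safety physician code the free text and then follows one of two routes.

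- **Code outside the listed symptoms.** "Other symptoms of ISR that were coded into the terms beyond the list of pre-specified symptoms will be summarized under" a single Other symptoms heading. If someone reports several such terms, "the participant will be counted once in the summary of" that heading for the treatment concerned. The individual terms go to a listing: "The free texts entered by the participant, and the coded terms for" these symptoms are to be shown there.
- **Code equal to a listed symptom.** In that case "the participant will be counted only once based on the maximum severity and duration across the pre-specified symptom entries and the coded terms".

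Table 5-9 defines ISR duration differently: "Duration from first instance of the symptom to the last instance of the symptom within the treatment period". For the first 30 days this is the last ISR date minus the first, plus one, from diary data at participant level. For several diary entries on one day, SAP 5.6.4 also uses a maximum: "then the worse severity and maximum duration" enter the summary.

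**The concern.** The free-text field is there to catch reactions that the diary does not name. Once those reactions are coded, the natural summary is by coded term. With one pooled row, five participants who report the same new reaction look the same in the ISR tables as five participants with unrelated complaints. A cluster would have to be found by reading the listing.

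The second matter is separate and concerns listed symptoms only. A participant may tick a symptom on some days and type it on others. If a duration is derived for each kind of entry and the larger is kept, the result can be shorter than the first-to-last span that Table 5-9 prescribes. Any error shortens the reported reaction, which favors the device. Two programmers working from the same SAP could also produce different tables.

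**Working it through.** The plan gives no figure to reproduce here. The check compares its rules with each other.

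**1. Pooled row: incidence**

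Inputs are the one-row rule and the one-count-per-participant rule in SAP 5.6.4. As an illustration, assume k independent unlisted terms, each with rate p. Neither value is in the documents. The pooled rate is 1 - (1 - p)^k.

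| k | p | Pooled rate |
|---|---|---|
| 3 | 1% | 1 - 0.99^3 = 3.0% |
| 3 | 2% | 1 - 0.98^3 = 5.9% |
| 3 | 5% | 1 - 0.95^3 = 14.3% |

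With the 147 treated participants assumed in SAP section 3, the middle line is 147 x 0.0588 = 8.6 expected participants. One reaction at 5.9% would give the same row as three different reactions at 2%. The row cannot separate them, although the listing can.

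**2. Merged listed symptom: duration**

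Let the ticked entries run from day a1 to day a2 and the typed entries from day b1 to day b2.

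- Larger of two durations: max(a2 - a1 + 1, b2 - b1 + 1)
- Table 5-9 on the combined entries: max(a2, b2) - min(a1, b1) + 1

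| Ticked | Typed | Larger of two | Table 5-9 |
|---|---|---|---|
| Days 1-10 | Days 3-6 | 10 | 10 |
| Days 1-4 | Days 5-12 | max(4, 8) = 8 | 12 - 1 + 1 = 12 |
| Days 1-7 | Days 5-12 | max(7, 8) = 8 | 12 |
| Days 1-5 | Days 8-12 | 5 | 12 |
| Days 1-15 | Days 16-30 | 15 | 30 |

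In the second line the shortfall is (12 - 8)/12 = 33%.

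All 216,225 ordered pairs of intervals within Days 1-30 were enumerated. The larger-of-two rule never exceeded the Table 5-9 span. The two are equal when one interval contains the other. Otherwise the larger-of-two rule is shorter, by at most 29 days (one entry on Day 1 and one on Day 30: 1 day against 30). The rules differ in 62% of pairs. That is a count of possible patterns, not a forecast of how often the trial would meet them.

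**3. Pooled row: duration, if Table 5-9 were applied to it**

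SAP 5.6.4 gives no duration rule for this row. Suppose the first-to-last rule were applied to it as it stands. Dryness on Day 2 only and numbness on Day 25 only would then become one reaction of 25 - 2 + 1 = 24 days, although each lasted 1 day. This result is conditional on that reading.

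**The case against.** Unlisted reactions are not lost. Under protocol 9.4 the treating investigator reviews the diaries and decides whether an ISR qualifies as an AE. SAP Table 5-8 then tabulates TEAEs by system organ class, preferred term and severity. The coded terms are also listed, so a rate can be counted by hand. A reader might infer that no unlisted reaction can ever get a rate of its own. The documents do not support that. What stands is narrower: a reaction left as an ISR has no by-term summary, and the AE route depends on the investigator's judgment.

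A reader might also infer that the planned durations are wrong. The SAP states rules, not durations, and the merge rule agrees with Table 5-9 whenever one set of entries spans the other. The wording is open as well: maximum may govern severity alone, which would leave duration as the span over all entries. Against that, protocol 9.4 has the diary record presence and severity, not duration, and the same-day rule in SAP 5.6.4 explicitly attaches maximum to duration. The larger-of-two reading is therefore the more natural one, but it is not certain.

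Nor do the documents show that durations in the pooled row will be too long. The SAP is silent on that row, and section 1 places table specifications in a separate document, which might add sub-rows by term. The SAP itself commits only to one count per participant, with the terms in a listing.

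Finally, these are descriptive summaries with no test or decision rule attached, and the documents do not say how common free text will be. That limits the weight of the point.

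**Conclusion.** Two separate and modest points hold.

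- **Incidence and severity.** As written, the ISR summary tables give no per-term incidence or severity for an unlisted reaction, although protocol 10.3.2 plans a summary by symptom. This follows directly from SAP 5.6.4.
- **Duration.** If the merge rule means the larger of two durations, it conflicts with Table 5-9 and understates duration whenever neither set of entries spans the other. It never overstates. Examples are 8 against 12 days and 5 against 12 days. If maximum governs severity only, there is no conflict, but the SAP should say so.

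The merge rule has no bearing on rates of unlisted reactions. The pooled-duration problem arises only if Table 5-9 is applied to the Other symptoms row. No realistic size for the trial as a whole can be given, because the documents do not state how many participants will enter free text. No effectiveness conclusion is affected. This is a worthwhile improvement to a safety table, not a threat to the trial.

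**What to change.** Revise SAP 5.6.4 as follows.

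1. Recode free text in the daily records before any ISR endpoint is derived.
2. Add an entry coded to a listed symptom to that symptom's daily record, using the worst severity for the day. Derive duration once from the combined record by the Table 5-9 rule, and drop the separate maximum-duration wording for merged entries.
3. Tabulate entries coded to other terms by coded term, with maximum severity and duration for each term.
4. Keep any other symptom as a participant count only, without duration.

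The same edit can settle a related mismatch. The pre-specified symptoms named in SAP 5.6.4 number eight and omit swelling, which is among the nine in protocol 9.4. Read literally, free text coded to swelling would fall under Other symptoms.

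The cost is a few sentences and some extra table rows. The codes are already produced for the listing and no new data are needed. The downside is a longer table with some low-count rows.
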